## **7.6 Subject Completion and Individual Subject Discontinuation**

### **7.6.1 Subject Completion**

A subject will be considered as having completed the study after completing participation in the Week 18 visit (end of the 2-week follow-up period).

Note: See [Section 7.6.3](#) for subjects who discontinue study drug or withdraw early from the study.

See [Section 10.3.6](#) for information regarding follow-up of unresolved events.

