#### 9.4.6 Week 6 Visit

This visit will be scheduled on the day of the first hemodialysis session of the week.

At the Week 6 visit, the following activities/procedures will be performed:

- Vital signs
- Dry weight
- Dialysis treatment review
- AE review
- Rescue therapy (ESA rescue and RBC transfusion) review
- Laboratory procedures:
  - CBC
  - Chemistry
  - Iron indices
  - Heparin
  - C-reactive protein
  - VEGF
- Concomitant medication review
- Collect study bottle and all remaining study drug tablets remaining from the primary efficacy period (last dose to be taken on day of Week 6 visit)
- Dispense one bottle of vadadustat (first dose to be taken day after Week 6 visit)
- Subjects should be questioned regarding dosing compliance
- Review dosing instructions and remind subjects that they may be contacted by telephone to discuss dose adjustment depending on central lab Hb result
- If central lab Hb result obtained from this visit supports dose adjustment based on dose adjustment guidelines, contact subject for dose adjustment ([Section 8.2.5](#))

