2.2 Secondary Objectives and Endpoints

The secondary objectives of this study are:

- To assess the safety, tolerability, pharmacokinetics (PK), and pharmacodynamics (PD) of oral vadadustat once daily dosing in Japanese subjects with anemia secondary to DD-CKD during the 6-week, primary efficacy period
- To evaluate the effect of dose adjustments and demonstrate the maintenance effect on Hb during a 10-week dose-adjustment and maintenance period
- To assess the time to reach the target Hb range from baseline

The secondary endpoints that will be used to assess these objectives include the following:

- Time to reach target Hb level of 10.0-12.0 g/dL from baseline visit (Day 1)
- Mean Hb levels at the end of the primary efficacy period (Week 6) and at the end of the dose adjustment and maintenance period (Week 16)
- Proportion of subjects who achieve target Hb 10.0-12.0 g/dL at the end of the dose adjustment and maintenance period (Week 16)
- Mean change in Hb between pre-treatment and the end of the dose adjustment and maintenance period (Week 16)
- Mean change in hematocrit, red blood cell (RBC) count, and reticulocyte count from baseline to the end of the primary efficacy period (Week 6) and the end of the dose adjustment and maintenance period (Week 16)
- Mean change in iron indices (i.e., iron, total iron-binding capacity [TIBC], transferrin saturation [TSAT], and ferritin) and hepcidin from baseline to the end of the primary efficacy period (Week 6) and the end of the dose adjustment and maintenance period (Week 16)
- Proportion of subjects requiring rescue with RBC transfusion from baseline to the end of the primary efficacy period (Week 6) and the end of the dose adjustment and maintenance period (Week 16)
- Proportion of subjects requiring rescue with erythropoiesis-stimulating agents (ESAs) from baseline to the end of the primary efficacy period (Week 6) and the end of the dose adjustment and maintenance period (Week 16)
- Number of dose adjustments from baseline to the end of the dose adjustment and maintenance period (Week 16)
- Plasma concentration profile of vadadustat and its metabolites using pre-dose sample from Week 4

The safety endpoints that will be used to assess these objectives include the following:

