Study drug treatment will be administered during a 6-week primary efficacy period. See the protocol section 8.2.4 for information on study drug administration. The primary efficacy period includes fixed-dose treatment to establish a dose-response relationship. However, if Hb level increase rapidly or if the Hb levels exceeds 13.0 g/dL, the study drug dose can be decreased or interrupted (see the protocol section 8.2.4).

After completing the primary efficacy period, subjects will continue to a 10-week dose adjustment and maintenance period (see the protocol section 8.2.5). Subjects receiving placebo will be switched to vadadustat, and study drug dose will be adjusted to achieve a target Hb of 10.0-12.0 g/dL based on dose adjustment guidelines (see the protocol section 8.2.5).

Vadadustat treatment will stop after the dose adjustment and maintenance period has been completed (Week 16) and subjects will continue in a 2-week follow-up period (Week 17-18).

For subjects who were not being treated with ESAs, the clinical and safety assessments will be performed as described in the protocol section 9.4 and as listed in the protocol Appendix A. For subjects who were being treated with ESAs prior to study entry, the clinical and safety assessments will be performed as described in the protocol section 9.5 and as listed in the protocol Appendix B.

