4.2 General Presentation Considerations

Pre-treatment Hb is defined as the average of 3 Hb values obtained prior to treatment based on most recently 2 qualifying screening Hb values and the Hb value at the baseline visit (Day 1). 'Pre-treatment' for other variables is defined as the last available pre-treatment assessment. In general, this is the value at the Baseline Visit. 'End of Treatment (EOT)' is defined as the assessment on the EOT form labeled as 'Week 16 Visit', even if other values closer to Day 113 are available. For the analysis purpose, only actual visit will be used and hence EOT will be presented as "Week 16". In the summary table, EOT of early withdrawal will not be counted but only be displayed in the listing for reference purpose. 'Treatment Day' will be calculated relative to start of dosing at Baseline Visit (i.e. Treatment Day = Assessment Date - Baseline Visit Date + 1).

Continuous data will be summarized in terms of the mean, standard deviation (SD), median, minimum, maximum and number of observations, unless otherwise stated. The minimum and maximum will be reported to the same number of decimal places as the raw data recorded in the database. The mean and median will be reported to one more decimal place than the raw data recorded in the database. The SD will be reported to two more decimal places than the raw data recorded in the database. In general, the maximum number of decimal places reported shall be four for any summary statistic.

Categorical data will be summarized in terms of the number of subjects providing data at the relevant time point (n), frequency counts and percentages. Any planned collapsing of categories will be detailed in the SAP text and the data displays.

Percentages will be presented to one decimal place. Percentages will not be presented for zero counts. Percentages will be calculated using n as the denominator. If sample sizes are small, the data displays will show the percentages, but any textual report will describe frequencies only.

Changes from baseline in categorical data will be summarized using shift tables where appropriate.

P-values greater than or equal to 0.001, in general, will be presented to three decimal places. P-values less than 0.001 will be presented as “<0.001”.

Confidence intervals will be presented to one more decimal place than the raw data.

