4.7.3 Secondary Efficacy Variables

The analysis population for efficacy will be MITT and PP population.

Change from baseline visit to Week 6 in HB (g/dL).

The following summaries will be provided:

- A summary of actual value of Hb by treatment group at baseline and week 6. A summary of the change (absolute and percent) from baseline in Hb by treatment group at week 6. 1st and 3rd quartiles (Q1, Q3) as well as the mean, SD, median, minimum, maximum and number of observations will be shown. P values for overall comparison and treated groups vs. placebo on change from baseline will also be presented.
- The effect of treatment in terms of the change from pre-treatment to Week 6 in Hb will be analyzed using a one-way analysis of covariance (ANCOVA). The statistical model will assess the main effect of treatment, adjusted for Baseline. Least-squares (LS) means for each treatment and their 95% confidence intervals (CIs) will be

presented. Three post-hoc pairwise comparison, i.e., Placebo vs 150 mg, placebo vs 300 mg, and placebo vs 600 mg, will be done. Unadjusted one-way analysis of variance (ANOVA) will be performed for sensitivity.

- The simple linear regression between the change from Baseline to Week 6 in Hb and dose will be calculated. The regression coefficients and their standard errors, p-values of test of regression parameters and their 95% CIs will be presented. The test of slope parameter will be used to evaluate dose response relationship.
- A waterfall plot for absolute Hb change from baseline for each treatment group at week 6.
- A summary of the number and percentage of subjects who achieved a ≥ 1 g/dL increase in Hb from baseline average will be provided by treatment group.

Time to reach target Hb level

Time to reach target Hb level of 10.0-12.0 g/dL from baseline is defined for subjects with Hb <10.0 g/dL at the baseline visit as following:

First post-treatment assessment date with value of Hb ≥ 10.0 and ≤ 12.0 g/dL – the baseline visit date +1. If target Hb level is not achieved, last Hb assessment date will be used as censored date.

A summary of time to reach target Hb level will be provided for subjects with Hb <10.0 g/dL at the baseline visit by treatment group.

A by-subject listing will be provided.

Hb within target Range

A summary of the number and percentage of subjects within target Hb 10-12 g/dL at the end of the dose adjustment and maintenance period (Week 16) will be provided by treatment group.

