4.7.4 Exploratory Efficacy Variable

Time in Therapeutic Range (TTR) for Hb from week 6 to week 20

The half-time interpolation method will be used to calculate TTR for Hb. The total time of follow-up with Hb in target range of 10.0 to 12.0 g/dL is divided by the total time. Half the time between two tests is allocated to the first Hb value, and half to the second Hb value.

A summary of TTR for Hb will be provided by treatment group.

A by-subject listing of TTR for Hb will be provided by treatment group

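### SAP 4.7.4 runs time in therapeutic range to a Week 20 that is not scheduled, and SAP 4.7.3 carries time to target past the Week 6 switch under randomised-group labels (minor; the primary analysis is unaffected)

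*SAP*

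**What the plan says.** **Time in therapeutic range (TTR).** The heading in SAP 4.7.4 reads "Time in Therapeutic Range (TTR) for Hb from week 6 to week 20". The method is half-interval allocation: the time between two consecutive Hb tests is split equally between their values, and time in 10.0 to 12.0 g/dL is divided by total time. SAP Amendment 1 edited this section and kept the Week 20 end point.

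**Schedule.** SAP 3.1 says "Vadadustat treatment will stop after the dose adjustment and maintenance period has been completed (Week 16", followed by a 2-week follow-up. Protocol 7.6.1 says "A subject will be considered as having completed the study after completing participation in the Week 18 visit". The schedules in Protocol Appendices A and B end at Day 127 (Week 18). The matching objective in SAP 2.2 is to "demonstrate the maintenance effect on Hb during a 10-week dose-adjustment and maintenance period".

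**Time to target.** In SAP 4.7.3 this "is defined for subjects with Hb <10.0 g/dL at the baseline visit". The event is the first post-treatment Hb within 10.0 to 12.0 g/dL, and "If target Hb level is not achieved, last Hb assessment date will be used as censored date". The summary is by treatment group, which SAP 4.4.2 makes the randomised group. At Week 6 the site is to "Dispense one bottle of vadadustat (first dose to be taken day after Week 6 visit" (Protocol 9.4.6; 9.5.7 agrees). From then on Protocol 8.2.5 adjusts the dose in every group.

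**Fisher tests against placebo (SAP 4.7.3).** The target-range test is fixed at Week 6. The test for a rise of at least 1 g/dL follows a cumulative summary and names no time point. The RBC transfusion/ESA test follows summaries to both Week 6 and Week 16 and does not choose between them.

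**The concern.** Each of these summaries has an end point that is wrong, open or unstated, in a study where randomised, placebo-controlled treatment ends at Week 6 and all study drug ends at Week 16.

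- TTR would mix on-drug and off-drug Hb without saying so, although the objective it serves concerns the dose-adjustment and maintenance period.
- In the time-to-target table, later events in the placebo row are responses to vadadustat. Later events in the 150 mg and 300 mg rows can arise at doses other than the label. Someone choosing a Phase 3 starting dose could misread those rows as placebo or fixed-dose results.
- A Fisher test run to Week 16 would compare early with delayed vadadustat, not vadadustat with placebo.

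**Working it through.** **1. The plan's own calendar.** Protocol 6.2 gives 22 and 29 weeks in total: 4 + 6 + 10 + 2 = 22 and 11 + 6 + 10 + 2 = 29. Both reproduce. Time after baseline is 6 + 10 + 2 = 18 weeks. With study day = 7 × week + 1, Weeks 6, 16 and 18 are Days 43, 113 and 127, as in the appendices. Week 20 would be Day 141, which neither schedule contains.

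**2. TTR weights.** With visits every 2 weeks, each interior visit carries 2 weeks and each end visit 1 week.

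| Window | Weights, in visit order | Total | Off-drug time | Weight of Week 18 value |
|---|---|---|---|---|
| Weeks 6–16 | 1, 2, 2, 2, 2, 1 | 10 | 0 | none |
| Weeks 6–18 | 1, 2, 2, 2, 2, 2, 1 | 12 | 2/12 = 16.7% | 1/12 = 8.3% |

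The method allocates no time after the last test, so a nominal Week 20 end yields Weeks 6 to 18 in practice.

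**3. Size of the shift.**

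- In range through Week 16, out at Week 18: 11/12 = 91.7%, against 10/10 = 100% when ended at Week 16.
- Visit windows: Protocol 9.4.9 and 9.5.10 place follow-up 2 weeks after the end-of-treatment visit. With gap g = 14 ± 3 days and Weeks 6 and 16 each ± 3 days, TTR = 1 − (g/2)/(D16 − D6 + g). The extremes are 1 − 8.5/(64 + 17) = 89.5% and 1 − 5.5/(76 + 11) = 93.7%.
- General case: let A be the in-range weight out of 10 over Weeks 6–16. If exactly one of the Week 16 and Week 18 values is in range, the shift is (A + 1)/12 − A/10 = (10 − 2A)/120. The largest absolute value is 10/120 = 8.3 points, at A = 0 or A = 10.

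**4. Time to target.** Scheduled post-baseline Hb visits are Weeks 2, 4, 6, 8, 10, 12, 14, 16 and 18, nine in all. In the placebo row, 3 reflect placebo (Weeks 2, 4, 6), 5 vadadustat (Weeks 8 to 16) and 1 is off drug (Week 18). So 6 of 9 follow the switch.

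Under the increase rule in Protocol 8.2.5, a subject who stays below 10.0 g/dL can move from a 150 mg start to 300, 450 and 600 mg after Weeks 6, 10 and 14, or from a 300 mg start to 450 and 600 mg after Weeks 6 and 10.

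Illustration with assumed counts: if 2 placebo subjects reach target by Week 6 and 4 more after the switch, the row moves from 2/12 = 17% to 6/12 = 50%. With 8 eligible subjects it moves from 25% to 75%. Twelve is an upper bound, because only subjects below 10.0 g/dL at the baseline visit count.

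**5. Fisher window.** Illustration with assumed counts for the 1 g/dL rise, two-sided: 1/12 on placebo against 7/12 on 600 mg by Week 6 gives p = 0.027. To Week 16, with 10/12 on 600 mg, 3, 5 or 8 of 12 in the former placebo group give p = 0.012, 0.089 or 0.64. The window can change the answer in either direction.

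**The case against.** **TTR is exploratory, and Week 18 could have been meant.** This stands in part. The documents do not settle whether 16 or 18 was intended, and SAP 4.7.2.3 runs another summary to Week 18. Week 16 is preferred because it matches the 10-week objective.

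**The shift can look larger than it is.** A reader might infer that off-drug values can move TTR by as much as 15 points. Across all 128 in/out patterns, every shift above 10 points, including that maximum, has Week 18 agreeing with Week 16. Those shifts are interval reweighting; a discordant off-drug value moves TTR by at most 8.3 points. A reader might also take 14 weeks as the denominator, giving 4/14 = 28.6% off drug and a ceiling of 12/14 = 85.7%. Half-interval allocation does not support that, because no time follows the last test.

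**Ending at Week 16 is not clean either.** This stands. In the former placebo group the Week 6 Hb is a placebo value and keeps 1/10 of the weight. Leaving out the early-withdrawal value, usually taken within a day of stopping (Protocol 7.6.3), could flatter subjects who leave with worsening anaemia.

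**Time to target follows the protocol.** This also stands. The endpoint has no end date, dose adjustment is itself an objective, no test is attached, and SAP 4.7.3 and 4.9.2 report dose by group and visit. The full-study summary is legitimate; what it lacks is a placebo-controlled companion and accurate labels.

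**The Fisher gap needs only clarification.** Agreed. A reader might infer that the SAP instructs testing against placebo at Week 16. It does not. Its other placebo comparisons with a stated time use Week 6: target range, Hb change, hematocrit, RBC and reticulocyte counts, CRP, VEGF and total cholesterol. For ESA use the stakes are small. Against 0/12, significance needs 5/12 on placebo (p = 0.037; 4/12 gives 0.093). Rescue ends participation, and the protocol assumes 10% dropout, about 1 in 12.

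**Conclusion.** The point holds as a minor one.

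- Week 20 is an error on the face of the current SAP. Followed as written, TTR covers Weeks 6 to 18 with 2 of 12 weeks off drug. For a completer in range through Week 16 and out at Week 18 the cost is 8.3 points (a score of 89.5% to 93.7% across the visit windows).
- The time-to-target rows cannot be read as placebo or fixed-dose results after Week 6, because two thirds of the scheduled post-baseline visits follow the switch.
- The two Fisher tests are ambiguous, not wrong.

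The TTR weights and visit counts rest on the documents' schedule. The event counts and the eligible number of 8 are assumptions for illustration. Nothing here touches the Week 6 ANCOVA, the step-down comparisons or the Week 6 regression, and SAP 4.7.1.4 intends no labelling claims from secondary variables.

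**What to change.** 1. **SAP 4.7.4.** Define TTR as Week 6 to Week 16. State how early withdrawals are handled: SAP 4.2 says "In the summary table, EOT of early withdrawal will not be counted", so say whether TTR ends at the last scheduled-visit Hb or uses the withdrawal value. Footnote that the Week 6 Hb, with 1/10 of the weight, is a placebo value in the former placebo group. Report Weeks 16 to 18 separately if wanted.
2. **SAP 4.7.3, time to target.** Add a summary by randomised group with all four groups censored at the Week 6 visit. Keep the full-study summary, which matches the protocol endpoint, but label the groups placebo-to-vadadustat and by starting dose, and note that the Week 18 Hb is off drug.
3. **SAP 4.7.3, Fisher tests.** State that the RBC/ESA and 1 g/dL tests run through the Week 6 visit. Keep the Week 16 proportions and the cumulative plot descriptive.

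The cost is SAP wording and some programming. No new data are needed and no planned Week 16 or Week 18 summary is lost.

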4.8 Safety Evaluation

All safety summaries and analyses will be based upon the safety population as defined in [Section 4.4](#).

4.8.1 Extent of Exposure

The extent of exposure will be summarized for the safety population. The following summary will be provided.

- A summary of the treatment duration (e.g. End Date of Administration - Start date of Administration +1) by treatment group and study visits.

A by-subject listing of start, end and duration of treatment will be provided.

4.8.2 Adverse Events

AEs will be coded using the Medical Dictionary for Regulatory Activities (MedDRA) Version 19.0.

Treatment-emergent adverse events (TEAEs) will be tabulated and are defined as those AEs that either start or worsen in severity on or after the date/time of first dose of study treatment and on or before the final protocol required visit. In general, it is Week 18 Visit and 14 days after the date of last dose of study treatment. The TEAEs are defined as those adverse events that started after first injection up to 14 days post-last dose.

Where AEs dates are missing or partially missing, AEs will be assumed to be treatment-emergent, unless there is clear evidence (through comparison of partial dates) to suggest that the AE started prior to the first dose of study treatment or more than 14 days after the last dose of study treatment.

Partial AE start dates will be imputed as follows:

1. If the year (and month and day) is unknown, the date will be imputed as the date of first intake of study treatment if this is possible (i.e., the event end date is not prior to treatment start date).
2. If the month and day is unknown then:
 - a. If the year matches the first dose date, then impute the month and day of the first dose date.
 - b. If the year is earlier than the first dose date or the first dose date is not available (subject is not dosed) and matches the year of informed consent date, then impute the month and day of the informed consent date;
 - c. Otherwise, assign January 1.
3. If the day is unknown then:
 - a. If the month and year match the first dose date, then impute the day of the first dose date.
 - b. If the month and year are earlier than the first dose date or the first dose date is not available (subject is not dosed) and matches the month and year of the informed consent date, then impute the day of the informed consent date;
 - c. Otherwise, assign '1'.

Partial AE stop dates will be imputed as follows:

1. If the year is unknown, the date will not be imputed and will be assigned a missing value.
2. If the month is unknown, then assign December.
3. If the day is unknown, then assign the last day of the month.

For all other settings (eg. year missing, but day and month available etc.), imputation strategies will be reviewed and decided in the ongoing data cleaning and sponsor meetings.

If the start and/or stop dates of medications other than study treatments are missing or partially missing, the dates will be compared as far as possible with the date of first study treatment administration.

If not specified, observed data approach will be performed.

The AE will be summarized using MedDRA system organ class (SOC) and preferred term (PT). All AE summaries will provide the number of subjects reporting at least one AE and the total number of events reported. The following summaries will be provided:

- A summary of the number and percentage of subjects reporting at least one TEAE, drug-related TEAE, TEAE leading to withdrawal, serious adverse event (SAE), drug-related SAE, SAE leading to withdrawal and death by treatment group.
- A summary of the number and percentage of subjects reporting a TEAE by treatment group, SOC, and PT

- A summary of the number and percentage of subjects reporting a drug-related TEAE by treatment group, SOC, and PT
- A summary of the number and percentage of subjects reporting a treatment-emergent SAE by treatment group, SOC, and PT
- A summary of the number and percentage of subjects reporting a SAE during the screening period Assessed as Related to Protocol Procedures by treatment group, SOC, and PT
- A summary of the number and percentage of subjects reporting a drug-related treatment-emergent SAE by treatment group, SOC, and PT
- A summary of the number and percentage of subjects reporting a drug-related TEAE leading to withdrawal by treatment group, SOC, and PT
- A summary of the number and percentage of subjects reporting a TEAE leading to withdrawal by treatment group, SOC, and PT
- A summary of the most common TEAEs by treatment group and PT (reported by >10% of subjects in any treatment group)
- A summary of the number and percentage of subjects reporting a TEAE by treatment group, severity, SOC, and PT
- A summary of the number and percentage of subjects reporting a TEAE by treatment group, relationship, SOC, and PT

AE summaries will be ordered alphabetically for SOC, and PT within SOC.

For each subject and each AE, the worst severity recorded will be attributed and used in the by-severity summaries. Similarly, the worst causality (most related to treatment) will be attributed and used in the by-causality summaries. If severity or causality is missing, data will be treated as observed.

A by-subject listing of all AEs (including non-treatment-emergent events) will be provided. This listing will be presented by treatment group and will include: center, subject identifier, age, sex, race, AE (SOC, PT, and verbatim term), date of onset, date of resolution, duration, severity, seriousness, action taken, outcome and causality.

The following AEs are defined as AEs of special interest. Summaries of the number and percentage of subjects reporting the following AEs will be provided.

- PT: “hyperkalemia” (MedDRA 10020646) or “blood potassium increased” (MedDRA 10005725)
- PT: “hyperuricaemia” (MedDRA 10020903) or “blood uric acid level increased” (MedDRA 10022891)
- PT: “Hypertension” (MedDRA 10020772) or “Blood pressure increased” (MedDRA 10005750) or “Blood pressure systolic increased” (MedDRA 10005760) or “Blood pressure diastolic increased” (MedDRA 10005739) or “Blood pressure ambulatory increased” (MedDRA 10005732) or “Blood pressure inadequately controlled” (MedDRA 10051128) or “Accelerated hypertension” (MedDRA 10000358) or “Essential hypertension” (MedDRA 10015488) or “Diastolic hypertension” (MedDRA 10012758) or “Systolic hypertension” (MedDRA 10042957) or “Malignant hypertension” (MedDRA 10025600)

- Standardised MedDRA Query (SMQ): “Cholestasis and jaundice of hepatic origin” (SMQ 20000009) or “Drug related hepatic disorders – severe events only” (SMQ 20000007) or “Liver related investigations, signs and symptoms” (SMQ 20000008)
- Standardised MedDRA Query (SMQ): “Ischaemic heart disease” (SMQ 20000043)
- SMQ: “Central nervous system haemorrhages and cerebrovascular conditions” (SMQ 20000061)
- SMQ: “Embolic and thrombotic events” (SMQ 20000081)
- SMQ: “Cardiac failure” (SMQ 20000004)
- SMQ: “Retinal disorders” (SMQ 20000158, narrow)

Serious adverse events that occur during the screening period and are assessed by the investigator as related to study procedures will be tabulated separately from treatment-emergent serious adverse events.

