4.4.1 Analysis Population for the Safety Analyses

The safety summaries and analyses will be based on the **safety population**. The safety population is defined as all enrolled subjects who receive at least 1 dose of study medication. In the event that a subject is allocated the incorrect study treatment as per the study randomization list, subjects will be summarized and analyzed ‘as treated’ i.e. by allocated treatment group.

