4.8.3 Deaths, Serious Adverse Events, and Other Significant Adverse Events

Other significant AEs are those AEs reported as leading to withdrawal from study. The summaries of SAEs and AEs leading to withdrawal from study are described in [section 4.8.2](#).

A summary of the number and percentage of deaths during the study will be provided by treatment group.

A summary of the number and percentage of subjects Adverse Events Leading to Death by treatment group, severity, SOC and PT

A by-subject listing of all deaths that occurred during the study will be provided.

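### Adverse event, SAE and death tables are not split at the Week 6 switch, so post-switch events of placebo subjects are counted under placebo

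*SAP*

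**What the plan says.** SAP 4.8.2 uses one treatment-emergent window. It opens at the first dose and closes "on or before the final protocol required visit", which it equates in general with Week 18 and 14 days after the last dose. The TEAE and treatment-emergent SAE tables have treatment group as their column, for example "A summary of the number and percentage of subjects reporting a TEAE by treatment group, SOC, and PT", and every AE table is to give "the number of subjects reporting at least one AE and the total number of events reported". For AEs of special interest the SAP says "Summaries of the number and percentage of subjects reporting the following AEs will be provided" and names no grouping. SAP 4.8.3 adds "A summary of the number and percentage of deaths during the study will be provided by treatment group", so deaths are counted over the study and not in the TEAE window. Screening SAEs judged related to study procedures have their own table.

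SAP 3.1 states that after the primary efficacy period "Subjects receiving placebo will be switched to vadadustat". Protocol 9.4.6 and 9.5.7 place the first dose from the new bottle on the day after the Week 6 visit. SAP 4.8.2 and 4.8.3 do not mention this change. The only attribution text, SAP 4.4.1, concerns subjects given the wrong treatment and places them as treated, "i.e. by allocated treatment group". The rules introduced by "Partial AE start dates will be imputed as follows" refer to the first dose and to consent, not to the switch.

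**The concern.** A placebo column that runs to Week 18 holds mostly time after the subject has left placebo. Events that begin on vadadustat appear there as placebo events, and any real difference between drug and placebo shrinks. SAP 4.8.2 also attributes the worst severity recorded, so an event that starts mild on placebo and becomes severe on vadadustat is shown as a severe placebo event.

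The secondary safety objective (SAP 2.2) refers to the 6-week primary efficacy period. That is also the only time when randomised placebo and vadadustat groups run side by side. No AE, SAE, special-interest or death table isolates it. Because there is no formal safety test, the displayed counts and percentages are the safety result, so it matters that a column describes the drug being taken.

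**Working it through.** The plan gives no figure to reproduce. The check compares the text first, then the scheduled time.

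**1. Where the SAP divides at Week 6**

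| Output | SAP section | Divided? |
|---|---|---|
| Protocol deviations | 4.3.2 | by period |
| Concomitant medication | 4.5 | separate summary after Week 6 |
| Excess Hb | 4.7.2.3 | by period |
| Liver abnormalities | 4.8.4.1 | by visit |
| Grade 3 laboratory abnormalities | 4.8.4.9 | by period |
| Blood pressure, heart rate, potassium outliers | 4.9.2 | by period |
| Rapid Hb rise (safety section) | 4.8.4.6 | no, but 4.7.2.3 gives a divided version |
| Blood pressure and heart rate outliers (vital signs) | 4.8.5.1 | no, but 4.9.2 gives a divided version |
| TEAEs, SAEs, special-interest AEs, deaths | 4.8.2, 4.8.3 | no, and no divided version |

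Blood pressure and potassium outliers are thus divided at Week 6, while the hypertension and hyperkalaemia event tables are not.

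**2. Time at risk in the placebo column**

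Inputs: Week 6, 16 and 18 visits on Days 43, 113 and 127 (protocol Appendix A); last first-period dose on the Week 6 visit day (protocol 9.4.6); 12 placebo subjects and 36 on vadadustat (protocol synopsis); no dropout.

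- Placebo: Days 1 to 43 = 43 days; 43/127 = 34%.
- Vadadustat: 113 − 43 = 70 days; 70/127 = 55%.
- Follow-up: 127 − 113 = 14 days.
- Post-switch in total: 84/127 = 66%.
- Twelve completers: 12 × 43 = 516 placebo subject-days against 12 × 70 = 840 vadadustat subject-days.
- Planned vadadustat time: 36 × 113 + 840 = 4,908 subject-days, of which 840 (17%) sit in the placebo column.

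Counting elapsed days instead (42, 70 and 14 of 126) gives 33% and 67%.

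**3. Illustration: event counts**

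Assume constant rates and one true rate ratio R for all doses. The ratio shown is 127R/(43 + 84R) if the drug rate persists through follow-up, or (113R + 14)/(57 + 70R) if follow-up is at the placebo rate.

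| True R | Shown, first form | Shown, second form |
|---|---|---|
| 1.5 | 190.5/169 = 1.13 | 183.5/162 = 1.13 |
| 2 | 254/211 = 1.20 | 240/197 = 1.22 |
| 3 | 381/295 = 1.29 | 353/267 = 1.32 |

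**4. Illustration: percentage of subjects**

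Assume R = 2, an assumed 6-week placebo risk p0, λ = −ln(1 − p0)/43, and the drug rate persisting through follow-up. The 6-week vadadustat risk is 1 − exp(−86λ). To Week 18 the placebo column is 1 − exp(−211λ), where 211 = 43 + 2 × 84, and the vadadustat column is 1 − exp(−254λ).

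| p0 | 6-week table | Table to Week 18 |
|---|---|---|
| 5% | 5% v 10% | 22% v 26% |
| 10% | 10% v 19% | 40% v 46% |
| 20% | 20% v 36% | 66% v 73% |

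Part of this narrowing comes from the longer window alone. With p0 = 20% and placebo continued to Day 127, the placebo risk would be 1 − 0.8^(127/43) = 48%, so the contrast would be 48% v 73%. The switch accounts for the rise from 48% to 66%.

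**5. The preliminary analysis**

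Protocol 11.3 promises 6-week efficacy and safety data. SAP 4.7.1.5 expects the 6-week data to match the final analysis, yet takes all data up to the calendar date on which the last randomised subject completes Week 6. Accrual time is not given. Assume even accrual over E days; mean post-switch time m is the mean of min(t, 84) for t from 0 to E, and its share of placebo-column time is m/(43 + m).

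| E (days) | m | Post-switch share |
|---|---|---|
| 60 | 30.0 | 41% |
| 90 | 44.8 | 51% |
| 180 | 64.4 | 60% |
| 365 | 74.3 | 63% |

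**6. Partial dates once a split exists**

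The Week 6 window is ±3 days, so the earliest post-Week 6 dose is Day 41, 40 days after Day 1 and always in a later calendar month than the first dose. SAP 4.8.2 then sets an unknown onset day in the switch month to the 1st, which is before the switch unless the switch is itself on the 1st. The present rules would therefore place nearly all such events in the placebo-controlled period.

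**The case against.** The strongest reply is that the layout may be settled elsewhere. SAP 6.1.1 refers to mock shells, which are not in the documents, and column layout is what shells specify. Protocol 11.3 also plans a 6-week safety summary, and the SAP says it should be read with the protocol. In addition, safety is descriptive, there are 12 subjects per arm, and the AE listing carries onset dates, so nothing is lost.

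Some of this stands. What the shells show is unknown, the primary endpoint is untouched, and the tables can be rebuilt from the data. But the SAP text requires no split, and the preliminary cutoff in 4.7.1.5 admits post-switch events of early enrollees, so the 6-week view is not secured.

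A reader might infer more than the documents support:

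- **That protocol 11.7 requires tables by dose at onset.** It asks for summaries by dose level without defining the term; the four randomised groups are arguably dose levels.
- **That protocol 11.4.1 settles attribution after the switch.** Its actual-treatment rule defines the safety population and does not mention the switch.
- **That the safety objective demands a placebo contrast.** It names the 6-week period but no comparator.
- **That the partial-date rules are already faulty.** They matter here only once the tables are divided.

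**Conclusion.** The point holds and should be fixed. As written, SAP 4.8.2 and 4.8.3 put post-switch events of placebo-allocated subjects in the placebo column and leave Weeks 1 to 6 unisolated for TEAEs, treatment-emergent SAEs, special-interest AEs and deaths. This is a misattribution that follows from applying the text, not merely a missing detail.

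The firm figure is the schedule-based one: 66% of a placebo completer's window is post-switch, 55% of it on vadadustat, assuming full follow-up. The diluted ratios, percentages and preliminary-analysis shares are illustrations that rest on assumed constant rates, a common rate ratio, assumed risks and assumed accrual. With 12 per arm, any of these tables will be imprecise.

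It would be too strong to say that the SAP ignores the switch throughout its safety analyses, since several outputs are divided by period. It would also be wrong to say that only event tables are undivided: SAP 4.8.4.6 and 4.8.5.1 are too, though with divided counterparts.

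**What to change.** Present the TEAE, SAE, special-interest AE and death tables in two periods, and state the grouping for the special-interest tables.

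1. **Period 1:** from first dose to before the subject's first dose from the bottle dispensed at Week 6, by the four randomised groups. For subjects who never take such a dose, run it to the end of the TEAE window so that no event is lost.
2. **Period 2:** from that dose to the end of the TEAE window, among subjects who took it, with former placebo subjects in a separate placebo-to-vadadustat column. For deaths, run to the end of the study.
3. **Worsening:** assign each TEAE by the date it started or worsened. An event that starts in period 1 and worsens in period 2 counts in period 2 at the worsened severity; period 1 shows only the worst severity reached in period 1.
4. **Partial dates:** amend the 4.8.2 rules to say how an onset date that could fall in either period is placed, identically in all groups, and footnote the number of such events by group.
5. **Preliminary analysis:** cut the safety data at each subject's own Week 6, so that SAP 4.7.1.5 agrees with protocol 11.3.

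A dose-at-onset table is optional. If produced, it should report events per subject-time at each dose, because one subject can contribute to several doses and percentages of subjects would have no clear denominator.

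The cost is SAP wording and one extra set of programmed tables, with no protocol change. Counts per period will be small. Item 3 assumes that the date of worsening is recorded; the AE listing described in the SAP shows onset and resolution dates only.
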